## 11.4. Analysis plan.

11.4.1. Outcome: Observed incremental area under the curve (iAUCobs) at 2 hours following each meal and snack will be evaluated via FGM using the Abbott Libre Pro, which captures interstitial glucose every 15 minutes. A sensor is inserted into the participant's arms. Participants will be blinded to glycemia tracings.

11.4.2. Covariates: Baseline characteristics. We will measure glycated albumin, a measure of glycemic control over a 2-3 week period. A questionnaire also will be administered to collect the following information:

- $\checkmark$  health characteristics of the participant and family members
- ✓ medication regimen
- general habits [dietary, sleep, physical activity, smoking, and bowel)]
  recent treatment with antibiotics
- ✓ birth history
- ✓ stress
- ✓ apnea risk

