# 10.0. Study Endpoints

We will validate the PNP algorithm for North American T2D and pre-diabetes patients in a 2-stage, repeated measures quasi-experimental trial in which participants serve as their own control. In stage 1, PNP methods will be used to conduct metabolic profiling and develop a patient-specific algorithm that predicts glycemic responses to food (iAUCpred). In stage 2, participants will consume, for 6 days, isocaloric diets (breakfast, lunch, dinner, and 2 snacks), which will be prepared and delivered daily, including 2 days each of low, moderate, and high glycemic load (GL) foods.

**10.1. Specific aim 1.** We will characterize iAUCpred and iAUCobs and describe differences between the two. Prior studies suggest that any difference between two AUCs less than  $\delta = 30\%$  of iAUCobs is not important and will be considered equivalent. Thus we will describe the equivalence of iAUCpred and iAUCobs by testing the null hypothesis of non-equivalence: H0:  $|iAUC_{pred} - iAUC_{obs}| \ge \delta$  and the alternative hypothesis of equivalence is H1: H0:  $|iAUC_{pred} - iAUC_{obs}| \le \delta$  overall and within each race/ethnicity. **10.2. Specific aim 2**. We will describe the extent to which the equivalence of iAUCpred and iAUCobs differs by whether or not the participant is prescribed metformin.

**10.3. Specific aim 3.** In preparation for future grant applications, we will establish the feasibility and acceptable of the research protocol.

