## 11.2. Stage 2 Feeding Validation\*

#### 10.2.1. Selection of foods for feeding study:

Using the nutrient composition data from derived from the Nutrient Data System for Research, we have established a database of 200 meals that vary in glycemic load (GL). From this database, we will select 60 meals, consisting of 4 breakfast, 4 lunch and 4 dinner meals, and 8 snacks from each of the following categories: low GL, moderate GL, and high GL. Participants will be directed to select 2 meals and 4 snacks from each GL category, or a total of 30 meals and snacks (5/day) that they would be willing to consume during Stage-2. Meals and snacks will be prepared off-site by PortableChef, a foodservice operation in New York City that specializes in tailoring meals and delivering them to clients. Food will be prepared from scratch, portioned to match their estimated energy requirements based on REE or Mifflin St. Jeor equations with a physical activity modifier of 1.3, using a commercial scale (TE10FT, Taylor Precision Products, Inc.; Oak Brook, IL), and delivered to the CTSI-CRC for participants to pick up or to the participant's home (Day-1 and Day-4).

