#### 11.2.2. Feeding study:

**Stage-2** feeding will take place on the 8th day Beginning the following day, for 6 days, participants will consume prepackaged meals and snacks. In order to limit the effects of meal order on glycemic response, each meal day will contain a random breakfast, lunch, dinner and 2 snacks from among those selected. The study personnel will call the subject on the 7th day to let the patient know about the feeding phase in detail (Telephone-4). Also, they will discuss about the feasibility and the barrier of using Abbott FGM, PNP app and FitBit. Also, the study personnel will ask the subject to charge the FitBit device. During stage-2 feeding phase, participants will continue to monitor meals, physical activity, sleep, medications, hunger, and stress with the PNP app. We also will obtain FitBit data on physical activity and sleep. A follow-up phone call (Telephone-5) to the subject will be made on to check that the subject is consuming the foods provided by the study and has been able to use the Abbott FGM without any issues. Any AEs or device incidents (DIs) will be recorded. To ensure that the glycemic response to meals and snack can be detected, participants will be directed to leave at least two hours between eating occasions. Although they will be asked to consume all foods and beverages provided, and nothing else (other than water for hydration), participants will be directed to record and report any deviation from the prescribed diet. On the day following the final meal, upon awakening (Day **14**), we will

Protocol version 02/23/2018 Study Protocol: s16-01059 NCT: NCT03053518 call the participants' (Telephone-**6**) and directed to remove the FGM, FitBit devices and return it to the investigators in a postage-paid sharps box provided to them. If the participants did not send the devices within 5 days after the study completion then we will call them 2 additional times (Telephone-**7** and Telephone-**8**).

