#### 11.5. Data analysis:

A descriptive analysis of all data collected will be performed using appropriate graphical and numerical exploratory data techniques. Data transformations will be performed to account for non-normal distributions. We also will conduct sensitivity analyses pertaining to the effects of baseline medication regimen (use of metformin or not). To address privacy concerns around microbiome sequencing, we implement metagenomic analyses using secure computation using secureseg platform (https://github.com/HCBravoLab/MicrobiomeSC). The median PPGR to standardized meals for each participant with 16S rRNA relative abundance at the species to phylum levels, MetaPhIAn tag-level relative abundance and relative abundance of KEGG genes will be examined using the Pearson correlation. We will cap relative abundance at a minimum of 1e-4 (16S rRNA), 1e-5 (MetaPhIAn) and 2e-7 (KEGG gene). For 16S rRNA analysis, the taxa with <20% of the features will be removed. The information obtained from this preliminary investigation of the data will be used as follows.

Specific Aims 1 and 2. We will compare iAUCpred and iAUCobs overall, and within racial/ethnic groups (i). using the equivalence test for paired data (TOST option in the PROC TTEST in R).

(ii). Specific Aim 3. We will develop a recruitment funnel to estimate the number of patients that must be approached to enroll and retain one participant. We will describe adherence to PNP app use, and adherence to the feeding component of the study.

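### Section 11.4.1 defines one iAUC per meal and snack, but section 11.5 names a plain paired TOST without stating the unit of analysis; applied to occasion pairs, that test would declare equivalence too often.

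*Protocol*

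**What the plan says.** Section 11.4.1 sets the outcome at the level of the eating occasion: "Observed incremental area under the curve (iAUCobs) at 2 hours following each meal and snack". The food-selection part of section 11.2 has each participant choose "or a total of 30 meals and snacks (5/day"), and section 11.2.2 separates them so that each response can be read: "participants will be directed to leave at least two hours between eating occasions". Section 7.0 plans 20 participants.

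Section 10.0 calls the study a "repeated measures quasi-experimental trial in which participants serve as their own control". Specific aim 1 introduces the margin with "Prior studies suggest that any difference between two AUCs less than" a delta of 30% of iAUCobs. It sets non-equivalence against equivalence, "overall and within each race/ethnicity", without saying whether the difference is per occasion, per participant or a mean.

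For aims 1 and 2, section 11.5 compares iAUCpred with iAUCobs "using the equivalence test for paired data (TOST option in the PROC TTEST in R"), overall and by racial/ethnic group. No participant-level summary, random effect or cluster adjustment is given for this test. The same section does reduce data to one value per person for the microbiome correlations: "The median PPGR to standardized meals for each participant".

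**The concern.** A paired TOST takes its standard error from the spread of the differences divided by the square root of the number of pairs, so the pairs must be independent. Thirty differences from one person are unlikely to be. They share one individualized model, that person's sensors and that person's metabolism, so a model that reads high for someone will tend to do so at many of their meals.

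If the differences are pooled, the interval is too narrow. The error then runs in the unwelcome direction: an algorithm whose mean prediction is off by the full margin is called equivalent more often than the nominal level allows. This is the test behind the study's main aim, and the plan repeats it in racial/ethnic groups, where the number of independent people is smaller still.

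**Working it through.** **Occasions and pairs.** Six feeding days with three meals and two snacks give 6 × 5 = 30, which reproduces the protocol's 30. Cross-check, reading the selection rule as two of each meal type: 3 glycemic-load categories × (2 + 2 + 2 + 4) = 30. For 20 participants, 20 × 30 = 600 pairs.

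**Inputs the protocol does not give (assumed).** One-sided level 5% for each test; intraclass correlation (ICC) of the differences 0.01 to 0.30; occasion-level SD of the difference 0.6 or 1.0 times mean iAUCobs; true bias exactly at +30%; margin treated as fixed.

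**Formula.** Design effect DE = 1 + (30 − 1) × ICC. Effective pairs = 600 / DE. Actual one-sided error of the pooled test ≈ Φ(−1.645 / √DE).

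| ICC | DE | Effective pairs | Formula | Simulated, pooled |
|---|---|---|---|---|
| 0.01 | 1.29 | 465 | 7.4% | 7.3% |
| 0.05 | 2.45 | 245 | 14.7% | 14.3–14.7% |
| 0.10 | 3.90 | 154 | 20.2% | 20.3–20.7% |
| 0.30 | 9.70 | 62 | 29.9% | 30.0–30.2% |

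The simulations used 20,000 runs per setting and normal differences with a participant effect. At ICC 0 the pooled test holds its level (4.7–5.0%). The same TOST on 20 participant means gave 4.7–5.3% over the tabulated ICCs.

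**Fewer usable occasions.** With 20 per person, DE = 1 + 19 × ICC, and the formula gives 6.6%, 11.9%, 16.7% and 26.2%.

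**Smaller groups.** Pooling inflates the error about as much. At ICC 0.10 and 0.30, with occasion SD 1.0, simulated error was 20.4% and 29.6% for 10 people, 20.5% and 28.1% for 6, and 19.5% and 25.3% for 4. Participant means gave 1.4–5.1% in these groups.

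**The relative margin (minor).** Delta is a percentage of iAUCobs, so it is itself estimated. For 20 participant means with the margin entered as a fixed number, observed CV 0.3–0.5 and predicted–observed correlation 0–0.9, simulated error was about 4–11% at the upper margin and 1–6% at the lower. Testing the two contrasts pred − 0.7 × obs and pred − 1.3 × obs gave 2.0–5.2%.

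**The case against.** The strongest reply is that pooling is nowhere stated. The protocol describes participants as their own controls, metformin use and race/ethnicity are properties of participants, and section 11.5 already forms one value per participant for another analysis. All of this fits a test on 20 participant pairs, whose level is sound. An SAP may exist and may say so. The study is also a pilot whose aims are to characterize and describe, with no decision tied to the result.

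Much of this stands. A reader might infer that the protocol commits to pooling 600 pairs; it does not, and both readings are open. A reader might also take 20% or 30% as this study's error rate. The protocol gives no level, ICC or variance, so those figures only illustrate. Nor should the enrolment table in section 7.0 be taken as fixing racial groups of 10, 6 and 4. Its Asian row shows 2 females and 4 males but a total of 4, and its 10 of 20 Hispanic participants do not match the 20–25% Latino target in section 6.3.

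What does not stand is that this is mere missing detail. The protocol itself fixes an occasion-level outcome and a named test for independent pairs, and the two do not fit until the unit is stated. The descriptive aim still carries formal equivalence hypotheses.

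A further fair objection is that averaging lets a person's over- and under-predictions cancel, although the algorithm is meant to predict responses to particular foods. That stands, and the remedy has to address it.

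**Conclusion.** The point holds as a mismatch between the defined outcome and the named test, with the unit of analysis left open. If the test is run on occasion pairs, equivalence is declared too often whenever prediction errors correlate positively within a person. That direction follows from the design. The size, about 7% to 30% against a nominal 5%, rests on the assumed level, ICCs of 0.01–0.30 and bias placed at the margin. If the pair is the participant, this problem disappears. The relative margin is a minor second point: it applies only if the margin is entered as a fixed bound, and its effect is modest and in both directions.

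**What to change.** In section 11.5:

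- Name the participant as the independent unit of the TOST. Preferably keep the occasions and fit a mixed model with a participant random effect, or use cluster-robust standard errors, with n − 1 degrees of freedom for n participants. Otherwise use participant means. The simulations cover participant means only. With all occasions recorded for everyone, the random-intercept model gives the same mean difference and, unless the between-person variance is estimated as zero, the same standard error.
- State that the test concerns mean bias, and report meal-level agreement alongside it.
- Test the margin as relative: claim equivalence only if both one-sided tests reject, showing mean(pred − 0.7 × obs) > 0 and mean(pred − 1.3 × obs) < 0. A ratio on the log scale with limits stated in advance is an alternative.
- For small racial/ethnic groups, report estimates with 90% intervals rather than an equivalence verdict.

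The cost is wording, wider intervals and lower power than pooling. Simulated power of the two contrasts on participant means, at zero bias and one-sided 5%, depends on the unknown participant-level SD of the difference (as a share of mean iAUCobs):

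| Participants | SD 0.28 | SD 0.36 | SD 0.40 |
|---|---|---|---|
| 20 | 98–99% | 89–92% | 82–85% |
| 10 | 73–81% | 49–55% | 38–42% |
| 6 | 37–45% | 19–22% | 14–15% |
| 4 | 16–21% | 8–10% | 6–8% |

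The overall comparison remains workable at these SDs. Groups of 10, such as the planned metformin split, depend on the SD, and groups of 6 or fewer cannot carry a verdict.

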#### 11.5. Data analysis:

A descriptive analysis of all data collected will be performed using appropriate graphical and numerical exploratory data techniques. Data transformations will be performed to account for non-normal distributions. We also will conduct sensitivity analyses pertaining to the effects of baseline medication regimen (use of metformin or not). To address privacy concerns around microbiome sequencing, we implement metagenomic analyses using secure computation using secureseg platform (https://github.com/HCBravoLab/MicrobiomeSC). The median PPGR to standardized meals for each participant with 16S rRNA relative abundance at the species to phylum levels, MetaPhIAn tag-level relative abundance and relative abundance of KEGG genes will be examined using the Pearson correlation. We will cap relative abundance at a minimum of 1e-4 (16S rRNA), 1e-5 (MetaPhIAn) and 2e-7 (KEGG gene). For 16S rRNA analysis, the taxa with <20% of the features will be removed. The information obtained from this preliminary investigation of the data will be used as follows.

Specific Aims 1 and 2. We will compare iAUCpred and iAUCobs overall, and within racial/ethnic groups (i). using the equivalence test for paired data (TOST option in the PROC TTEST in R).

(ii). Specific Aim 3. We will develop a recruitment funnel to estimate the number of patients that must be approached to enroll and retain one participant. We will describe adherence to PNP app use, and adherence to the feeding component of the study.

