# 2.0 IRB Review History. Approved by the IRB on 2/23/2018

# 3.0 Background information and specific aims

Type 2 diabetes (T2D) is an epidemic in the United States, affecting 29.1 million people. Poor glycemic control contributes to vascular complications of T2D (retinopathy, heart and kidney disease, stroke, and amputation) but recent clinical trials (ACCORD, ADVANCE, VADT) testing the potential benefits of aggressive medication management have been mostly neutral or negative. These trials targeted hemoglobin A1c (HbA1c) concentrations. However, there is growing evidence that glycemic variability (GV; from hyperglycemic peaks to hypoglycemic nadirs) may be a better treatment target than HbA1c. Although GV in early T2D is driven primarily by postprandial glycemic excursions, the results of dietary interventions to limit postprandial excursions have been mixed, perhaps because they used one-size-fits-all strategies such as low glycemic load (GL) diets that ignored the fact that individuals vary greatly in their glycemic response to food.

Several recent studies show that the composition and functional potential of the intestinal microbiota are critical factors in alucose homeostasis. With the Personal Nutrition Project (PNP); http://newsite.personalnutrition.org/WebSite/Home.aspx, [name] et al. devised the first personalized algorithm for predicting glycemic response to food. Using a machine learning approach, they developed a multidimensional profile that predicted food-specific glycemic excursions from gut microbiome data, various blood tests, questionnaires, and one week of mobile monitoring of food intake, glycemia, sleep, medication, physical activity, stress, and hunger. Subsequently, in a randomized trial among Israeli prediabetic individuals, the investigators successfully shown that tailored dietary recommendations from PNP algorithm were successful in reducing postprandial glycemic excursions.

[name] team at New York University School of Medicine will conduct an initial validation study of the PNP algorithm in a North American population with recently diagnosed T2D or pre-diabetes. This will be accomplished in a 2-stage, single-group feeding study in 20 individuals, including 10 participants managed with lifestyle alone, and 10 managed with lifestyle plus metformin.

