In early T2D GV is driven, primarily, by diet. While there is universal recognition that dietary management is key to successful T2D treatment, there is limited evidence regarding the best dietary approach(es) to take and the results of intervention studies have been mixed. Twelve recent (since 2008) randomized clinical trials of dietary interventions in those with T2D were found in the literature23-33. All used a 1-size-fits-all dietary prescription. However, the impact of diet on glycemia is influenced by many factors, including energy content, and the type and amount of carbohydrates, protein and fat in the meal; as well as how the foods were prepared and cooked. Also, each individual possesses their own unique physiologic response to food, based on their insulin resistance,  $\beta$ -cell function, gastrointestinal factors, and hepatic and peripheral glucose metabolism, which may be influenced by non-dietary factors including sleep, physical activity, medication/supplement regimen, and perhaps others 34, 35. None of the dietary studies that we reviewed tailored counseling to minimize postprandial glycemic excursions. Nearly all evaluated the intervention on the basis of HbA1c but, as discussed above, GV (evaluated in only 1 of the dietary intervention studies) may be a better predictor of downstream complications of the disease 32.

Of particular relevance to managing postprandial glycemia is the innovative work of the Personalized Nutrition Project (or PNP; http://newsite.personalnutrition.org/WebSite/Home.aspx). [name] et al. developed personally tailored double-blinded dietary counseling that lowered postprandial responses in a sample of Israeli individuals with prediabetes 36-38. With our pilot, we intend to validate this tailored approach in a US sample having recently diagnosed T2D. In a future trial, we will combine this tailored approach with our existing behavioral intervention and evaluate its efficacy for reducing GV, and minimizing metabolic memory effects.

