# 6.0. Inclusion and Exclusion Criteria

# 6.1. Inclusion criteria.

The study will be conducted in a diverse sample of 20 patients with early T2D or pre-diabetes who were managed by lifestyle modification or on metformin. The study inclusion criteria include:

- a. Age >21 years to <70 years
- b. Diagnosed with T2DM within 2 years or pre-diabetes with an HbA1c<8%
- c. Diabetes management by metformin or lifestyle intervention
- d. Willing to use their own or a study loaner smart phone to monitor multiple factors influencing glycemic response to glycemia (e.g., sleep, physical activity, diet, stress, medication, and hunger)

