### 7.0. Study-Wide Number of Subjects.

We will recruit a total of 20 individuals to the study. Preliminary data indicate that we will have access to 200 potentially eligible patients from which we must recruit only 10.0% to enroll 20.

	Sex/Gender							
Ethnic Category	Females	Males	Total					
Hispanic or Latino	2	8	10					
Not Hispanic or Latino	6	4	10					
Ethnic Category: Total of All Subjects *	8	12	20					
Racial Categories								
American Indian/Alaska Native	0	0	0					
Asian	2	4	4					
Native Hawaiian or Other Pacific	0	0	0					
Black or African American	4	6	10					
White	2	4	6					
Racial Categories: Total of All Subjects *	8	12	20					

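### Section 11.5 correlates microbiome features with test-meal glucose response without adjusting for metformin, so a feature can appear linked to response if both it and the response differ by metformin status

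*Protocol*

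**What the plan says.** Section 3.0 of the protocol plans the sample as "10 participants managed with lifestyle alone, and 10 managed with lifestyle plus metformin", and section 7.0 confirms the total: "We will recruit a total of 20 individuals to the study". Eligibility in section 6.1 admits both kinds of management: "Diabetes management by metformin or lifestyle intervention".

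The microbiome analysis is in section 11.5. Its unit is the participant: "The median PPGR to standardized meals for each participant with 16S rRNA relative abundance", followed by MetaPhlAn tag-level abundance and KEGG gene abundance. The measure of association is given at the end of that sentence: "relative abundance of KEGG genes will be examined using the Pearson correlation". No covariate, stratum or partial correlation is mentioned.

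Shortly before, the same paragraph commits to "sensitivity analyses pertaining to the effects of baseline medication regimen (use of metformin or not"). It does not say which analyses these cover or how they are done. The paragraph describes its contents as preliminary.

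Section 4.0 lists, among the things that may influence a person's response to food, "non-dietary factors including sleep, physical activity, medication/supplement regimen". Section 11.4.2 collects the medication regimen by questionnaire.

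**The concern.** With one value per participant and no stratum named, the natural reading is a single correlation over all 20 people. That sample is planned as two equal groups that differ in treatment, and also in whatever led to treatment. A pooled Pearson correlation combines the association within the groups with the association between the two group means. If the metformin group has a different average PPGR and also a different average abundance of some taxon, the between-group part alone produces a correlation.

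Such a feature would mark metformin status. It would say nothing about why two people on the same management respond differently to the same meal, which is the person-specific signal of interest here. Section 12.0 foresees further work on the microbiome and glucose response from stored samples, so a misleading list of correlates could be carried forward. Neither the planned data transformations nor a multiplicity correction removes this bias.

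**Working it through.** The protocol gives no alpha, effect size or power for these correlations, so there is no stated figure to reproduce. What follows is an illustration under assumptions.

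**Inputs from the protocol:** 20 participants (section 7.0), planned 10/10 by metformin (section 3.0), unadjusted Pearson correlation on one value per person (section 11.5).

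**Assumptions:** normal variables with equal within-group SD; no link between abundance and PPGR within either group; group means differing by d1 SD in abundance and d2 SD in PPGR; two-sided 5% test.

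**Induced correlation.** With half the sample in each group, the group means contribute ½ × ½ × d1 × d2 = d1·d2/4 to the covariance, and d²/4 to each variance. So

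r = (d1·d2/4) / √[(1 + d1²/4)(1 + d2²/4)].

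- d1 = d2 = 0.5: 0.0625/1.0625 = 0.06
- d1 = d2 = 1: 0.25/1.25 = 0.20
- d1 = d2 = 1.5: 0.5625/1.5625 = 0.36
- d1 = 2, d2 = 1.5: 0.75/√(2 × 1.5625) = 0.42
- d2 = 0, any d1: 0

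**Critical values.** |r| = t/√(df + t²), with t the 97.5% point of the t distribution:

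- unadjusted, 18 df: 0.444
- partial correlation given metformin, 17 df: 0.456
- within one group of 10, 8 df: 0.632

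**Share of null features reaching p<0.05** (simulation, 100,000 data sets per setting):

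| Abundance shift d1 (SD) | PPGR shift d2 (SD) | Induced r | Unadjusted | Adjusted for metformin |
|---|---|---|---|---|
| 0.5 | 0.5 | 0.06 | 5.7% | 5.1% |
| 1 | 1 | 0.20 | 13.5% | 5.1% |
| 1.5 | 1.5 | 0.36 | 37.6% | 4.9% |
| 2 | 1.5 | 0.42 | 51.8% | 5.0% |
| 2 | 0.5 | 0.17 | 11.4% | 5.0% |
| 2 | 0 | 0 | 5.1% | 5.0% |
| 0 | 1.5 | 0 | 5.0% | 5.0% |

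The last two rows show that both shifts are needed. If either is zero, the unadjusted correlation keeps its nominal error rate. The adjusted correlation keeps it in every setting.

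**The case against.** **The paragraph already deals with metformin.** The promised sensitivity analyses stand in the same paragraph, just before the microbiome text, and nothing confines them to other analyses. They may well be meant to cover these correlations, and their form could be set out in an SAP that is not at hand. This weakens the point but does not remove it. The promise names neither target nor method, and the unadjusted correlation remains the result that the protocol specifies.

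**Both shifts are assumed.** This is correct. Section 4.0 says only that medication is among factors that may influence response, and it does not name metformin. Aim 2 asks whether the agreement of predicted and observed response differs by metformin, not whether the level of response does. No section says that metformin changes gut taxa. The net PPGR difference could be near zero if the treatment and the reason for prescribing it act in opposite directions. The 5% threshold is also an assumption.

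**A reader might infer that any taxon differing by metformin status will look linked to glucose response.** The documents do not support that. Without a PPGR difference there is no bias, even with a 2 SD shift in abundance, and with 0.5 SD in both the excess is under one percentage point. Nor do they support the claim that metformin is ignored altogether.

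**Adjustment could remove a real effect.** The worry is that metformin might act on PPGR through the microbiome. But metformin then lies upstream of the microbiome, so adjusting for it keeps the association within each group, which is the one of interest. Only the between-group part is set aside, and the unadjusted value stays on view.

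**The analysis is exploratory.** It serves none of the three aims and is called preliminary. That lowers the severity; it is no reason to leave the method as it is.

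**Conclusion.** The point holds in a conditional form and at low severity. Section 11.5 specifies an unadjusted correlation in a sample planned half and half on metformin. Where both PPGR and abundance differ by metformin status, that correlation can show a link present in neither group. Under equal shifts of 0.5, 1 and 1.5 SD in both, about 6%, 13.5% and 38% of such null features would pass p<0.05 instead of 5%. These rates apply only to features with shifts of that size. They rest on assumed shifts, normality, the 10/10 split being achieved, and a 5% threshold that the protocol does not state. The equivalence and feasibility analyses under the three aims are not affected.

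**What to change.** In section 11.5, state that each abundance–PPGR association will be reported as a Pearson correlation adjusted for metformin use (a partial correlation, equivalent to correlating deviations from the metformin-group means), with the unadjusted value beside it. State also that any claim that a feature is linked to PPGR rests on the adjusted value. This would settle how metformin is handled for the microbiome correlations.

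The cost is a sentence or two. The variable is already collected, and all 20 participants stay in the analysis. One residual degree of freedom is lost (17 instead of 18), which raises the critical |r| from 0.444 to 0.456. Relying on separate within-group tests would cost far more, since with 10 people |r| must exceed 0.632. Within-group scatterplots are still a useful display for any feature that is reported.

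### A pass on the paired TOST would show small mean bias; it cannot by itself support validation of a predictor meant to tell foods apart within a person

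*Protocol*

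**What the plan says.** Section 10.0 states the purpose: "We will validate the PNP algorithm for North American T2D and pre-diabetes patients". Stage 1 is to "develop a patient-specific algorithm that predicts glycemic responses to food". Sections 3.0, 4.0 and 5.0 explain why. The algorithm is described as predicting excursions food by food, its intended use is tailored dietary advice, and a future trial is to build on this pilot.

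Aim 1 (10.1) will characterize predicted and observed iAUC "and describe differences between the two". It then sets an equivalence margin: "Prior studies suggest that any difference between two AUCs less than" 30% of iAUCobs is treated as unimportant. The hypotheses compare the absolute difference with that margin. They do not say whether the difference is a mean or belongs to a single meal.

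Section 11.5 names the method for Aims 1 and 2, overall and within racial/ethnic groups: "using the equivalence test for paired data (TOST option in the PROC TTEST in R". It also says "A descriptive analysis of all data collected will be performed using appropriate graphical and numerical exploratory data techniques". The one correlation it names relates responses to standardized meals to microbiome abundance, not predicted to observed iAUC.

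The data are finer than the test. Under 11.4.1 the outcome is iAUC "at 2 hours following each meal and snack will be evaluated via FGM". Stage 2 runs for six days with five eating occasions a day, "including 2 days each of low, moderate, and high glycemic load (GL) foods".

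**The concern.** Tailored advice depends on knowing which foods raise a given person's glucose more than others. A paired equivalence test asks something else: whether predictions are right on average. An algorithm can be right on average and carry no information about foods, because over-prediction for some cancels under-prediction for others.

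Mean bias is a reasonable first question when an algorithm is carried to a new population in 20 people. The difficulty is the gap between that question and the word used in 10.0. If 10.1 and 11.5 are followed as written, the one formal result available to support a validation statement would be nearly or exactly the same for a good predictor and for one that misorders foods. The planned trial of tailored advice could then rest on a property that was never tested.

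**Working it through.** **Inputs from the protocol.** 20 participants (7.0); 30 eating occasions each (11.2), so up to 20 × 30 = 600 pairs; 2 days × 5 occasions = 10 occasions per person at each of three GL levels (10.0); margin 30% of iAUCobs (10.1); paired TOST (11.5).

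**Assumptions.** The protocol gives no significance level, variance or unit of analysis. I take one-sided 5% for each TOST side, read the margin as 30% of mean iAUCobs, and try both units. There is no power or precision figure to reproduce.

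**Step 1: what the test can see.** Let d(i,j) = predicted minus observed for participant i at occasion j. A participant's mean difference is mean predicted minus mean observed. Reassigning that person's predictions among occasions leaves mean predicted unchanged.

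- Participant means: all 20 values are unchanged, so the verdict is identical.
- Pooled meals: the overall mean difference is unchanged; only the SD, and so the standard error, moves.
- Log scale, one option under the transformations planned in 11.5: each participant's mean log difference is also unchanged.

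A small example: observed responses are 0.5, 1.0 and 1.5 at low, moderate and high GL. Correct predictions give differences 0, 0, 0. Exchanging the low and high predictions gives +1.0, 0, −1.0. Both means are 0.

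**Step 2: how much scatter passes.** At zero mean difference the TOST passes if SD < 0.30 × √n / t(0.95, n−1), in units of mean iAUCobs.

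- n = 20: 0.30 × 4.472 / 1.729 = 0.776.
- n = 600, meals treated as independent: 0.30 × 24.495 / 1.647 = 4.46.

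**Step 3: illustration.** Observed iAUC was simulated as lognormal for 20 × 30 occasions in 27 settings: GL ratios 0.5:1:1.5, 0.7:1:1.3 and 0.8:1:1.2; between-person log-SD 0.20, 0.35 and 0.50; within-person log-SD 0.3, 0.5 and 0.7. None of these values is in the protocol. Three predictors were compared: ideal (the true person-by-GL mean), reordered (each person's ideal predictions shuffled among foods) and swapped (low and high exchanged).

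- Participant means: the reordered and swapped predictors passed in at least 99.9% of trials, and all three predictors shared the same verdict in every trial in which they were compared.
- Pooled meals: the reordered and swapped predictors passed in 100% of trials.

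**Step 4: a form that could discriminate.** Suppose the 10.1 margin were applied to per-meal relative differences, averaged by participant. In the example of Step 1, the swapped predictor gives +200%, 0% and −67%, a mean of +44%, which exceeds 30%. Simulated pass rates:

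- Within-person log-SD 0.3, across the three GL ratios in the order above: ideal 100/100/100%, swapped 0/96/100%, reordered 0.1/100/100%.
- Log-SD 0.5: ideal 14–16%, swapped at most 0.1%, reordered at most 1.4%.
- Log-SD 0.7: all fail, because even the ideal predictor has an expected relative difference of exp(0.49) − 1 = 63%.

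This form detects misordering only when GL contrasts are large and noise is low. As noise grows it also rejects the ideal predictor.

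**Step 5: would added measures help?** The 95% CI of the within-participant slope of observed on predicted, clustered by participant, lay above 0 in 93–100% of trials for the ideal predictor, 2–7% for the reordered and 0% for the swapped. A predictor using GL alone, with no personal data, also gave a CI above 0 in 98–100% of trials, with mean bias of about 0–2% at low and high GL. Slope and bias by GL therefore expose misordered foods but do not show that a prediction is personal.

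**The case against.** The strongest reply has four parts.

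- **The analysis plan may cover it.** Correlations and calibration slopes are usual contents of a statistical analysis plan, which is not at hand. Their absence from the protocol is no fault, and the point does not rest on it. It rests on what the protocol does fix: a test that answers a narrower question than the aim it serves.

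- **No rule equates a pass with validation.** This stands. A reader might infer that the protocol would declare the algorithm validated on a TOST pass. It does not say so. Section 3.0 calls the study an initial validation, Aim 1 also promises to describe differences, 11.5 plans description of all the data, and plots of predicted against observed by food would fit within both.

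- **The test is neither empty nor blind in every form.** This also stands. One constant for every person and food passed on participant means in only 58–70% of simulated trials when the between-person coefficient of variation was 0.5. The per-meal relative form in Step 4 can sometimes detect misordering, although the protocol does not specify it. To say that the TOST can never detect a bad predictor would go too far.

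- **The simulated rates are illustrative.** Agreed. The reordered and swapped predictors have no mean bias by construction. They show what the test cannot see and do not forecast how the algorithm will perform. The algebra in Step 1 needs no variance assumption, and Step 2 needs only the significance level and the reading of the margin.

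A further fair criticism is that slope and bias-by-GL checks can be met by a generic GL table, the kind of uniform approach that the protocol criticizes. That is correct, and it is why a GL-only benchmark is part of the change proposed.

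**Conclusion.** The point holds in a limited form. The paired TOST in 11.5 bounds mean bias, or its log-scale analogue. A pass cannot by itself support the 10.0 aim of validating a patient-specific predictor of response to food.

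On participant means, the indifference to reassignment among foods is exact. On pooled meals it is exact for the mean difference, and the scatter needed to fail is very large. The thresholds of 0.78 and about 4.5 times mean iAUCobs assume zero mean difference, one-sided 5% and a margin of 30% of mean iAUCobs. The simulated rates rest further on variances and GL ratios that the protocol does not give.

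This is worth correcting before the results are interpreted. It does not make the TOST wrong as a first test, and it does not show that the investigators intend to claim validation from that test alone.

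**What to change.** In 10.1 and 11.5, keep the TOST and label it a test of mean bias. State that any validation statement will also rest on the paired Stage 2 occasions, through:

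- (a) the within-participant correlation and calibration slope of iAUCobs on iAUCpred, with 95% CIs that account for clustering by participant;
- (b) iAUCpred minus iAUCobs at each GL level;
- (c) the same within-participant agreement compared with that of a GL-only predictor, or assessed within GL level, because (a) and (b) alone can be met without personal data.

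Model detail can go in the statistical analysis plan. With 20 participants, these estimates should be reported as descriptive.

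The cost is a few sentences of protocol text and a little more analysis of data already planned, with no new visits, samples or participants. The downside is that a favourable conclusion becomes harder to reach.
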